The main variable of interest and primary outcome measure of the treatment effect is the mucosal-plaque index (MPS). It consists of the sum of a four-point plaque score (PS) and a four-point mucosal score (MS). For the PS, score of 1 suggests no visible plaque, score of 2 suggests plaque is barely visible, score of 3 suggests a moderate amount of plaque, and score of 4 suggests large amount of plaque almost covering the whole surface of teeth. For the MS, score of 1 suggests normal mucosal, score of 2 suggests mild inflammation, score of 3 suggests medium inflammation, and score of 4 suggests strong inflammation. For both scores, if in doubt between 1 and 2, they are instructed to score 1. If in doubt between 3 and 4, they are instructed to score 4.

The index is designed to evaluate oral health and oral hygiene in groups of individuals, developed for use in institutions. This makes it a suitable index to be used when conditions are not optimal to assess the patient. In prison, dental staff have limited equipment and poor light compared to conditions at a dental clinic. It was therefore important to use an index designed to be used outside of dental clinics with less optimal conditions for oral examination.

The secondary measures of outcome are based on questionnaire responses. These are questions asked both prior to treatment and during the follow-up period, and measures changes in how the prisoner perceives his oral health, how his routines are for maintaining his teeth, and his intake of food and drinks. How these questions are formulated can be seen from the questionnaire directly. These questions are designed to measure behavioral changes because of the intervention. As the questions are identical at each meeting point, any difference in changes across the treatment and control group is likely to be a result of the intervention. Importantly, even though the MPS-index may not measure a significant change in oral hygiene, such behavioral changes may still be of great importance. For example, even though a prisoner does not change his cleaning routines and is unable to improve his plaque score, a reduction in intake of unhealthy food and drinks may still reduce the damage on his teeth. Likewise, an improved perception about their oral health, may still improve self-esteem, even though there is no reduction in plaque score.

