In addition, as a secondary outcome measure, dental staff take notes of how many times the prisoner asks questions about his teeth. If the intervention successfully increases the prisoner's interest in his own oral health, we could expect more questions about his oral health.

Basic methodology:

The study is a randomized control trial (RCT), testing an MI-based intervention on oral health (oral hygiene) for prisoners in Rogaland County, Norway. More details about the population and the intervention follows in subsequent sections.

We randomize prisoners into treatment or control groups, blocking at prison level, using the randomization tool at www.randomizer.org. See the randomization section for more details on the randomization process. Moreover, we blind prisoners from treatment status, and dental staff is either blind to treatment when doing the oral examinations, or the oral examination is conducted by two dental staff independently of each other. See the blinding section for more details on blinding.

Study design and procedures:

Geographic region

The geographic region of this study is Rogaland County in southwestern part of Norway. Rogaland County is the wealthiest county in Norway measured in terms of household income (2019, SSB). Despite being one of the wealthiest counties in Norway, growing up in Rogaland is similar to growing up in other counties in Norway. An important reason for this is the unitary and federally funded school system, with only a few ideological or pedagogical based private schools. This gives all children growing up in Norway similar opportunities to obtain an education and subsequently enter the labor market.

Research population

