Prisoners are not informed whether they are in the treatment or control group and are therefore blind to treatment status. Dental staff are blind to prisoners' treatment status at the time of the first oral examination and questionnaire. The prisoner's treatment status is revealed just after this. Hence, dental staff collects all data prior to knowing the prisoner's treatment status, and only learn this when they start the MI-based conversation. When prisoners are back at T1 and T2 for follow-up oral examinations and questionnaires, dental staff might still remember whether the prisoner was treated or not. To partially account for potential bias in the oral examination (assessment of oral hygiene and inflammation in gingival), there are two independent assessments of this at T1 and T2. See pre-specification of analytical decisions for more on this.

Power calculations:

We have used GPower and Optimal Design to conduct power calculations.

GPower is used to calculate required sample size for simple comparison of means for the main variables of interest between the treatment and control group, without considering that data is collected at multiple sites. We choose the non-parametric Wilcoxon-Mann-Whitney test, set alpha to 0.05 and required power to 0.8. There is uncertainty concerning the effect size. Previous literature offers some guidance, however there are several important differences to our study. MI-interventions to change oral health have previously been tested on periodontist patients and patients with mental illness, populations that differ from ours. For our main variable of interest, level of plaque, these studies have found effect sizes ranging from 0.286 to 1.213¹. However, one should note that these studies have used different indexes to measure plaque, questioning the comparability of the effect sizes. Setting the power estimate to a moderate level in this range, to 0.5,

¹ An effect size of 0.286 was found after 12 weeks in Brand et al. (2012), whereas an effect size of 1.213 was found in Godard et al. (2011).

our required sample size is 106 prisoners. If we use a more conservative estimate and set it to the lowest effect size observed in the studies referred to above (0.286), the required sample size is 320.

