To test the overall effects of the intervention on our primary and secondary outcome variables, we will conduct non-parametric Wilcoxon Mann-Whitney U-tests. Given the ordinal outcome variables, we consider this test as more appropriate alternative relative to traditional two independent sample t-tests. We will compare the means of the treatment group and the control group at T0, T1 and T2. At T0 we expect no differences in means as no intervention has occurred. At T1 and T2 we expect better scores for the treatment group relative to the control group. Notably, our primary interest will be the difference in means at T1, as we expect more missing data at T2 due to prisoners being released from prison. However, for the intervention to have a long-lasting improvement on the prisoner's oral health, it is important that the intervention successfully enables the prisoner to make lasting changes. If we do not find a statistical difference between the treatment and the control group at T2, however, it may be hard to tell whether this is due to the intervention effect fading out or lack of power. See power analysis for more details on this, in which we show effect sizes possible to detect at different number of observations, given that power is set to 0.8 and number of sites is set to 4. As drop-out increases at T2, the higher the effect size must be for us to be able to detect any statistical difference between the groups.

Moreover, we are going to run multiple ordinal logistic regressions where we include selected covariates (see below). Running regressions allow us to control for the baseline measures of plaque

by using the baseline score of the outcome variables as a lagged dependent variable, in addition to including other covariates likely to correlate with the treatment and to explain variation in the dependent variable. For robustness purposes we also run regressions with fixed effects, controlling for unobserved individual time-invariant characteristics.

Covariates:

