The main covariate included in the analysis is the pre-intervention MPS index score. For our secondary outcome variables, the equivalent pre-treatment observation is used as covariate to control for pre-intervention status. We include these as they are likely to explain a lot of the variation in the outcome variable. Furthermore, we include a dummy variable for each prison, to control for prison-specific variation, and a dummy variable for the person who completed the MI-intervention with the prisoner.

As described below, we will also conduct heterogeneous analysis. Covariates that are relevant for such analysis (HASI and depressive symptoms) will also be included in the overall analysis.

Other covariates may be included, however given that we have successfully randomized prisoners, they should not affect our results. For robustness purposes, we will run analysis that include individual-specific covariates such as age, education, and length of prison sentence.

Heterogeneous analysis:

We will study heterogeneous effects of the intervention depending on their baseline score of the primary outcome variable. Those who score high on level of plaque have the greatest improvement potential. However, they might also be those with the least interest in taking care of their oral health. As motivational interviewing is designed to also motivate those who are not motivated, they may still experience the greatest improvement from the intervention.

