As mentioned under the section for blinding, there will be two assessments of the MPS index score at T1 and T2, as dental staff are not blind to their second and third meeting with the prisoner. If the original examiner finds no improvement in the MPS-index score, the second examiner's score will be ignored. If the original examiner finds an improvement, the average score of the original examiner and the second examiner will be used, however the second examiner's score will not be used to increase the average score above the assessment of the original examiner. We consider this a conservative approach. If the original examiner is not part of the team that evaluates at T1 and T2 (for example if the prisoner has been transferred to a different prison, or due to sick absence), an average score of the two assessments by the new examiners will be used.

Another concern is potential differences in how oral examinations and the intervention is conducted across multiple sites. To minimize differences, all dental staff have undergone the same MI training and practice. All oral examinations are being conducted by trained professionals, and they have gone through a calibration day prior to the start of the data collection. Moreover, they will continuously be provided guidance from a professional MI-consultant. In addition, we track the time they spend on each MI-based conversation.

Recruitment of prisoners may also be slightly different from one prison to another, as in half of the prisons it is done by prison officers and the other half it is done by dental staff. Prisoners may perceive the question of whether they want to participate or not differently, depending on whether they are asked by a prison officer compared to a dental staff. Moreover, the language assessment may also be different. Although this occurs independent of the randomization, it might lead to a difference in the population recruited to the experiment across prisons. Unfortunately, we could not have the same recruiter across all prisons. However, the information provided to the prisoners is the same across all prisons. This also applies to the instructions concerning language assessment; in the case of uncertainty about Norwegian language skills, the same screening question is asked across prisons, and the same evaluation criteria is being used.

Conclusion

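### The second MPS examiner at T1 and T2 must be independent but need not be unaware of the arm, so both primary-outcome scores can come from staff who know it

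*Combined protocol and SAP*

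**What the plan says.** Treatment effects and measurements makes MPS the primary outcome. It is a four-point plaque score plus a four-point mucosal score (range 2 to 8, higher is worse), judged in prison with limited equipment and poor light. Statistical model specification adds that "our primary interest will be the difference in means at T1".

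On who scores it at follow-up:

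- **Basic methodology** says that staff are blind at the examination or that "the oral examination is conducted by two dental staff independently of each other", and refers to the blinding section.
- **Blinding** says that T0 data are collected before the arm is revealed, that staff learn it when the MI conversation starts, and that they may remember it at T1 and T2. The remedy is worded as follows: "To partially account for potential bias in the oral examination (assessment of oral hygiene and inflammation in gingival), there are two independent assessments".
- **Other issues** gives the reason for the second score: "as dental staff are not blind to their second and third meeting with the prisoner". If the original examiner finds no improvement, the second score is dropped. If there is an improvement, the two are averaged, with a limit on the second score's influence. If the original examiner is absent, two new examiners are averaged.
- **Intervention** has dental staff deliver the MI conversation, which includes an agreed change plan. **Covariates** lists "a dummy variable for the person who completed the MI-intervention with the prisoner", so the deliverer's identity should be in the data.

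No section says what the second or new examiners may know, how the arm is concealed from them, or whether MPS is scored before the follow-up questionnaire and any talk with the prisoner.

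**The concern.** Independence and blindness protect against different things. Two independent scores reduce random rating error. They do nothing about a tendency, shared by two people who both know the arm, to score treated prisoners more kindly. A visual score with four coarse grades per component, taken in poor light by members of the staff group that delivers the intervention, leaves room for such a tendency.

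At stake is the T1 comparison. Two aware examiners would comply with the plan as written. Because awareness is not recorded, a reader of the results could neither exclude the bias nor gauge it.

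**Working it through.** **1. The roles side by side**

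| Examiner at T1/T2 | Role in the plan | Condition on knowing the arm |
|---|---|---|
| Original | Examined at T0; learned the arm when MI began | None; knowledge is acknowledged |
| Second | Independent assessment | None stated |
| New (pair) | Used if the original examiner is not on the team | None stated |

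**2. Why independence is not enough**

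Write examiner k's score as truth + b_k × arm + e_k, where the e_k are independent with variance σ². A plain average has error variance σ²/2 and bias (b_1 + b_2)/2.

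- Both aware with the same b: the bias is still b.
- Only the second examiner unaware (b_2 = 0): the plain average carries b/2.
- The unaware score alone carries no such bias.

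**3. The plan's own figures**

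The plan gives no figure for rater bias. Its effect sizes serve as a yardstick. A noncentral-t calculation with efficiency 3/π, 1:1 allocation, one-sided alpha 0.05 and power 0.80 gives totals of 106 (d = 0.5) and 320 (d = 0.286), as stated in Power calculations. Two-sided, the totals would be 134 and 404. The simulation below therefore uses 160 per arm and shows both one-sided and two-sided rates.

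**4. Illustrative total bias**

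Assume that an aware examiner scores treated prisoners 0.25 to 0.5 points lower and that MPS has an SD of 1 to 2. Shift/SD is then:

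- 0.25/2 = 0.125
- 0.25/1.5 = 0.17
- 0.5/1.5 = 0.33
- 0.5/1 = 0.5

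This is the shift when both examiners are aware. The plan's lowest literature effect is 0.286.

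**5. What an unaware second examiner changes under the planned rule**

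The simulation assumes no true effect, a latent mean of 4.5 with SD 1.2, within-person change with SD 0.7 and rater error with SD 0.5. An aware examiner scores a treated prisoner 1 point lower with probability p. There are 1,500 runs per cell and a Mann-Whitney test at 0.05. The limit in the rule is read as stopping the second score from enlarging an improvement.

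| p | Aware | Mean shift (points) | False positives, one-sided | Two-sided |
|---|---|---|---|---|
| 0 | neither | 0.00 | 5.3% | 5.1% |
| 0.1 | original only | -0.061 | 9.2% | 6.0% |
| 0.1 | both | -0.070 | 11.1% | 7.0% |
| 0.2 | original only | -0.124 | 19.3% | 11.3% |
| 0.2 | both | -0.144 | 23.3% | 14.4% |
| 0.3 | original only | -0.185 | 32.5% | 22.2% |
| 0.3 | both | -0.220 | 40.0% | 27.4% |

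The share of the shift that remains when only the second examiner is unaware is 0.061/0.070 = 87%, 0.124/0.144 = 86% and 0.185/0.220 = 84%. This is well above the one half of a plain average, because the original score always enters and stands alone when it shows no improvement.

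The limit can also be read literally, as stopping the second score from raising the result above the original examiner's. One-sided rates are then 15.9%, 32.8% and 54.9% with both aware, and 12.7%, 29.9% and 48.7% with the original examiner only. The ordering is unchanged.

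**The case against.** The plan is open about the weakness. Blinding says staff may remember the arm and calls the remedy partial. The second examiner may often be unaware in practice: the stated route to knowledge is memory of T0, and a colleague meeting the prisoner for the first time has none. All of this stands. It makes the point one of under-specification, not of contradiction or concealment.

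A reader might infer more, and the documents do not support it:

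- *That the second examiner is known to be unblinded.* The remark in Other issues that staff are not blind can be read as applying to those who are meeting the prisoner again. The text leaves the matter open.
- *That the plan equates two examiners with blinding.* The either/or in Basic methodology is a one-sentence summary that points to Blinding, which says the remedy is partial.
- *That the MI deliverer typically acts as second examiner.* Blinding has the staff who collect T0 data learn the arm when they start the conversation, so the deliverer is normally the original examiner. Split roles at T0 are not described, and the dummy in Covariates does not show that they occur.
- *That the T1 result is biased toward MI.* This needs awareness and an effect of awareness on scoring. Both are possible; neither is shown.

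It can also be said that the combining rule is conservative. It trims the bias but does not remove it: in the simulation a nominal shift of 0.10, 0.20 or 0.30 points per aware examiner still yields 0.070, 0.144 or 0.220.

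**Conclusion.** The point holds as a gap in the safeguard. The plan relies on two independent assessments at T1 and T2 without requiring the second or new examiners to be unaware of the arm. Both MPS scores can therefore come from aware staff, and independence would not remove a bias that they share.

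The size of any bias is unknown. The range of 0.125 to 0.5 SD rests wholly on an assumed shift and an assumed SD. It describes the total if both examiners are aware and should not be read as the cost of an aware second examiner. In the simulation, also on assumed inputs, making only that examiner unaware under the planned rule lowers one-sided false positives from about 11%, 23% and 40% to about 9%, 19% and 33%. Most of the original examiner's bias stays in the planned score, so the gain comes from analysing the unaware score separately.

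**What to change.** For T1 and T2 visits still to come:

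1. In Blinding and Other issues, define the second examiner as one of the staff already planned who did not conduct that prisoner's T0 visit or MI conversation and has no access to the allocation or change plan. Apply the same condition to new examiners where possible.
2. Have that person score MPS first, before the questionnaire or any conversation, and record whether they know the arm.
3. Pre-specify a T1 comparison on that examiner's score alone, reported beside the planned combined score.
4. Flag visits where no eligible colleague was present and visits completed before the change. The Conclusion says collection had already begun, so those scores cannot be re-ordered.
5. State in Basic methodology that two independent examinations are only a partial safeguard, as Blinding already says.

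The cost is wording, a changed order of tasks and one tick-box. Two examiners are already planned, but the plan gives no team sizes, so how often an eligible one will be present is not known. Some visits will lack an unaware score, and the added comparison will have fewer observations than the planned one.

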There are four prisons in Rogaland County, all of which are included in the study. Three prisons are categorized as high security prisons, and one is categorized as a low security prison. The main difference between high and low security prisons are the level of security measures, as prisoners in the low security prisons are allowed to move more freely within the prison. The low security prison is mainly used for less serious criminal offences, with a sentence time of between six months and two years. Those convicted to less than six months can apply to serve the time with an ankle bracelet, whereas those convicted for more than two years start serving in a high security prison. However, many high security prisoners are transferred to low security prison to serve the final part of their sentence. Hence, the population across prisons are likely to vary due to the severity of the criminal offence they have committed, especially across high and low security prisons. However, as those with the least serious criminal offences serve time with an ankle bracelet, and those with more severe convictions often serve the final part of their sentence in a low security prison, the populations may not be that different from each other.

The prison population may also contain prisoners who normally live outside of Rogaland County. If there is available capacity in the prisons in Rogaland County, and other parts of Norway have queues of people waiting to serve their sentence, they could end up serving their time in a prison in Rogaland County. Hence, the prisoners do not necessarily originate from or live in Rogaland County to serve their prison sentence in Rogaland County.

Recruitment is done somewhat differently across prisons, and different for those already imprisoned at the time of the start of data collection and those arriving in the prison during the data collection period. For those already imprisoned at the start of data collection, they are either informed about the study by prison officers or dental staff. We wanted this process to be done exclusively by prison officers, but capacity constraints forced us to use our own staff in two of the prisons. The information given is the same across all prisons, based on an information letter, which is also distributed to the prisoners. They then give their preliminary consent to participate within a couple of days after being informed.

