Dental staff also take note about how many times the prisoner ask questions about their findings from the oral examination. If the intervention raises their awareness to oral health, it is likely that those in the intervention group ask more questions during the follow-up period. Hence, this is also a secondary variable of interest.

We choose not to include questions about what sort of criminal offence the prisoner had committed and related questions that could challenge dental staffs perceived safety. For example, knowing you are talking to a sexual offender or murderer is likely to affect our dental staff negatively. When the prisoner signs the consent to participate in the study, he also approves that we are allowed to collect such data from the Norwegian Correctional Service. However, we are still not sure whether they will gain us access to such administrative data.

Randomization:

Randomization is done using the randomization tool www.randomizer.org. We randomize prisoners in the order that we receive lists of prisoners who have signed up to participate. Although this order

may not be random, the randomization process ensures that assignment to treatment and control group is. We block on prison level, to ensure a balance between treatment and control group in each prison. To ensure that there is not, by chance, an unequal assignment into treatment or control, we force the randomization to balance assignment into treatment and control for every fourth prisoner. That is, in groups of four, if the first two are assigned to the treatment group, the next two will be control group. To reduce the likelihood that dental staff in prison could guess the assignment of the next prisoner, we used every fourth prisoner rather than every second prisoner. The order that the prisoners meet may not be the same order as we randomize, further ensuring that dental staff may not guess whether the next prisoner is in the treatment group or not.

It would be very interesting to stratify the sample on gender, however we expect at most only to have a few observations on female prisoners. From early 2022, female prisoners will serve time outside of Rogaland County.

The unit of observation is at individual level. To ensure privacy of the prisoners, we do not collect any information that directly identifies them. However, given the detailed questionnaire, we do collect data that contains identifiable information.

Blinding:

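### Fixed blocks of four within prison could make up to a third of allocations certain before T0 scoring, if prisoners are met in randomised order

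*Combined protocol and SAP*

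**What the plan says.** The Randomization section of the pre-analysis plan stratifies by prison: "We block on prison level, to ensure a balance between treatment and control group in each prison". Within a prison, "we force the randomization to balance assignment into treatment and control for every fourth prisoner", illustrated by the remark that "in groups of four, if the first two are assigned to the treatment group, the next two will be control group". This is 1:1 allocation with two prisoners per arm in each block of four. No variation in block size is described. The sequence follows sign-up: "We randomize prisoners in the order that we receive lists of prisoners who have signed up to participate".

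The same section recognises that staff might guess the next allocation and gives two safeguards. The first is the longer block: "we used every fourth prisoner rather than every second prisoner". The second is that "The order that the prisoners meet may not be the same order as we randomize", which the plan presents as making sure that staff cannot guess.

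The Blinding section says that staff collect all T0 data without knowing the arm and "only learn this when they start the MI-based conversation". It provides two independent MPS assessments at T1 and T2, but none at T0. The Covariates section makes the T0 MPS the main covariate.

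The plan does not say whether dental staff know the block size, who holds the list, or how far meeting order departs from randomised order.

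**The concern.** Allocations are revealed to dental staff one prisoner at a time, as each T0 visit ends. With a constant block size, the allocations already seen can determine the ones still to come: the last place in a block is always fixed, and sometimes the last two are. A staff member who can work this out is no longer blind when scoring the next prisoner at T0.

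The T0 MPS depends on that blinding. It is the sum of two judged four-point scores, taken in poor light with limited equipment (Treatment effects and measurements), and no second assessor checks it. It enters the regressions as the main covariate. It is also the natural reference for the rule in Other issues, under which the second examiner's score at T1 or T2 counts only if the original examiner finds an improvement. A T0 score shaded by a guessed arm could therefore affect the adjusted models and, through that rule, the recorded T1 and T2 outcome.

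**Working it through.** The plan gives no predictability figure to reproduce, so the check starts from its description.

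**Inputs.** Fixed blocks of four, 2:2, separate by prison (Randomization). Arm revealed after each T0 visit (Blinding). 100 prisoners per prison for the simulations (the figure assumed in Power calculations). The displacement and list sizes below are assumptions, because the documents give none.

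**1. Worst case: prisoners met in randomised order, block size known, every allocation seen.** There are 6 equally likely orders.
- TTCC and CCTT fix positions 3 and 4: 2 certain places each.
- TCTC, TCCT, CTTC and CTCT fix position 4 only: 1 certain place each.
- Certain share = (2×2 + 4×1) / (6×4) = 8/24 = 33.3%.
- In general, for a block of size 2m the certain share is 1/(m+1): 50% for blocks of 2, 33.3% for 4, 25% for 6 and 20% for 8.
- Best-guess accuracy by position is 1/2, 2/3, 2/3 and 1. The mean is 2.833/4 = 70.8%.

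If the forced balance instead means a fair coin until one arm is full, the certain share is (½×2 + ½×1)/4 = 37.5%.

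**2. Meeting order differs from randomised order.** Reordering within a block leaves 33.3%. For reordering across blocks, the simulation takes a tracker who still assumes blocks of four in meeting order:

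| Assumed reordering | Prisoners for whom the tracker feels certain | Those calls that are right |
|---|---|---|
| Displacement SD 0.5 place | 34% | 94% |
| SD 1 | 35% | 80% |
| SD 2 | 36% | 65% |
| SD 4 | 37% | 57% |
| Full shuffle in lists of 8 | 36% | 65% |
| Full shuffle in lists of 20 | 37% | 55% |
| Full shuffle in lists of 100 | 37% | 51% |

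A tracker who knows exactly who is on a shuffled list of L prisoners has true certainty for 1/(L/2+1) of them: 20% for 8, 14% for 12 and 9% for 20.

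The plan's safeguard is therefore strong if the two orders differ widely and weak if they differ by about one place.

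**3. Random block sizes.** Meeting order equals randomised order, and the tracker knows the set of sizes but not which was drawn (600 simulated sequences of 100):
- fixed 4: certain 33.3%, best guess 70.8%;
- 4 or 6: certain 5.7%, best guess 69.1%;
- 4, 6 or 8: certain 2.4%, best guess 67.8%.

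**4. Imbalance.** A list that stops mid-block can be out of balance by at most half the block: 2 with blocks of 4, and 4 with blocks of up to 8.

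**The case against.** The plan foresaw guessing and took two steps against it. One third needs three conditions together: known block size, sight of every allocation in the prison, and meeting order equal to randomised order (or known block membership). The documents establish none of these. Randomisation follows sign-up lists, while formal consent comes only at the first meeting (Research population), so any refusal or no-show would break up the blocks as staff see them. All of this stands, and it makes one third a worst case under permuted blocks.

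A reader might infer that dental staff know the list order because they recruit. The plan does say that "capacity constraints forced us to use our own staff in two of the prisons", but this concerns prisoners already held when data collection began. New arrivals are informed by prison officers or health workers. Informing prisoners who consent within days is also not the same as knowing the order of the list.

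A reader might also infer that staff could steer entry through the Norwegian-language screening. The documents do not support this. Screening precedes randomisation, earlier allocations are revealed only after each T0 visit, and the test question is used in cases of doubt against predefined standards. Nor do they say that arrivals come slowly enough, or that teams are small enough, to keep the two orders close.

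Two further objections stand. The main comparison is an unadjusted Mann-Whitney test with primary interest at T1, so T0 reaches it only through the improvement rule. And the plan already admits that staff may remember the arm at T1 and T2, an exposure that a change of block size does not touch.

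**Conclusion.** The concern holds in conditional form. Up to 33% of allocations would be certain before T0 scoring, with 71% best-guess accuracy, for staff who meet all three conditions under permuted blocks of four. The plan's reliance on a different meeting order lowers this risk by an amount that it does not state, and so does not support its assurance that staff cannot guess.

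These figures measure predictability, not bias in the treatment effect, which cannot be sized from the documents. Nothing in them shows that staff tracked allocations, and they do not support reading one third as the share that staff actually know. The point is a cheap improvement to the protection of a baseline score that has no other safeguard, not a defect that invalidates the trial.

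**What to change.** For all remaining lists, draw block sizes at random from 4, 6 and 8 within prison, generate the lists away from the dental staff, and do not disclose the block sizes to them. State in the Randomization section who holds the list and what staff know, and replace the assurance about guessing with a statement that a different meeting order reduces the risk.

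This is a change of settings. The gain is in near-certain calls, from 33% to about 2% in the worst case; best-guess accuracy falls only to about 68%. The cost is a possible end imbalance of 4 instead of 2 per prison, most visible in the prison with 18 rooms. Data collection began in November 2021, so prisoners already randomised do not benefit. The report should say when the change took effect.
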